11.11 Criteria for Suspension in Accrual

The following is a list of criteria that will trigger suspension of accrual. In the even that such a suspension would occur, the Data and Safety Monitoring Committee (DSMC) would have to approve re-opening of accrual pending appropriate protocol revision (if needed):

 Interim/cumulative data for evidence of unacceptable rates and/or severity of studyrelated adverse events;

Specifically, The Data and Safety Monitoring Committee at Northwestern University will analyze toxicity data every 2 weeks. After every 5 patients an interim analysis will be performed to determine whether there is excessive toxicity. These analyses will be done separately within each arm. Excessive toxicity will be defined as any grade ≥ 4 neutropenia, grade ≥ 4 thrombocytopenia, or grade ≥ 3 organ toxicity (neurologic,

pulmonary, cardiac, gastrointestinal, genitourinary, renal, hepatic, cutaneous) with \geq 3 occurrences which is at least possibly related to the study regimen occurring in no more than 20%. Using a Bayesian approach with a non-informative (uniform) prior, it will be determined that there is excessive toxicity if the posterior probability of the toxicity rate being greater than 20% exceeds 80%. This will occur if there are 3 or more excessive toxicity events (as described above) out of 5 treated patients, 4 or more out of 10, 5 or more out of 15, 6 or more out of 20, 8 or more out of 25, or 9 or more out of 30. If, by 30 patients treated, the study has not been terminated for toxicity, it will continue to the goal accrual.

- o Incidence of >20% of any single excessive toxicity event (grade ≥ 4 neutropenia or thrombocytopenia OR grade ≥ 3 organ toxicity - minimum 10 patients treated)
- Treatment-related mortality of three or more patients
- Interim/cumulative data for evidence of efficacy according to pre-established statistical guidelines, if appropriate;
- o Clear lack of data quality, completeness, and timeliness;
- Clear deficits in performance issues of individual centers;
- Inadequacy of compliance with goals for recruitment and retention, including those related to the participation of women and minorities;
- Failure to adhere to the protocol;
- Presence of factors that might affect the study outcome or compromise the confidentiality of the trial data (such as protocol violations, unmasking, etc.);

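### Section 11.11 defines the excessive-toxicity event inconsistently, so how often accrual is suspended depends on how the rule is read

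*Combined protocol and SAP*

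**What the plan says.** Section 11.11 (Criteria for Suspension in Accrual) of the combined protocol and SAP sets a toxicity analysis after every 5 patients. The event is introduced thus: "Excessive toxicity will be defined as any grade ≥ 4 neutropenia, grade ≥ 4 thrombocytopenia, or grade ≥ 3 organ toxicity (neurologic". The list of organ systems (eight in all) is followed by a qualifier of three or more "occurrences which is at least possibly related to the study regimen occurring in no more than 20" percent.

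The decision rule is stated clearly. It is "Using a Bayesian approach with a non-informative (uniform) prior", and toxicity is excessive if the "posterior probability of the toxicity rate being greater than 20% exceeds 80" percent. The printed boundary begins at "3 or more excessive toxicity events (as described above) out of 5 treated patients", continues "4 or more out of 10, 5 or more out of 15, 6 or more out of 20, 8 or more out of 25", and ends at 9 of 30. The section also says: "These analyses will be done separately within each arm".

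The next trigger in the same list suspends accrual when any single excessive toxicity event exceeds 20% incidence, with at least 10 patients treated. It repeats the haematologic and organ categories but not the three-occurrence qualifier. The Study Summary describes a single-arm trial. Section 4.2 makes everyone who receives at least one treatment evaluable for toxicity, but does not say how a patient with several events is counted.

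**The concern.** This is the only formal statistical boundary for toxicity in the plan, and a committee could not apply it without first choosing a reading.

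- **Scope of the qualifier.** Three occurrences could mean within one patient, within one organ system across the trial, or over all organ toxicity in the trial. It could also attach to all three categories of event.
- **Rate inside the definition.** The 20% ceiling belongs to the decision rule. Inside the event definition it has no denominator and no function.
- **Counting unit.** The boundary sets events against patients, and nothing says that a patient counts at most once. It points back to the event as described earlier, so it inherits the faulty definition.
- **Arms.** There is only one.

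Two people applying the text to the same data could reach opposite suspension decisions.

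**Working it through.** **Inputs from Section 11.11.** Uniform prior; threshold rate 0.20; cutoff 0.80; printed boundary 3/5, 4/10, 5/15, 6/20, 8/25, 9/30; looks every 5 patients. The first four looks cover the 20 evaluable patients now planned.

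**Step 1: reproduce the printed boundary.** With one yes/no outcome per patient and x of n patients affected, the posterior is Beta(1+x, 1+n−x), and P(p > 0.20) = P(Bin(n+1, 0.20) ≤ x). For 2 of 5 this is 0.262 + 0.393 + 0.246 = 0.901, already above 0.80.

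| n | printed | P at one below printed | P at printed | smallest x with P > 0.80 |
|---|---|---|---|---|
| 5 | 3 | 0.901 | 0.983 | 2 |
| 10 | 4 | 0.839 | 0.950 | 3 |
| 15 | 5 | 0.798 | 0.918 | 5 |
| 20 | 6 | 0.769 | 0.892 | 6 |
| 25 | 8 | 0.869 | 0.941 | 7 |
| 30 | 9 | 0.849 | 0.925 | 8 |

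The printed numbers agree with the stated prior at 15 and 20 and are one too high at 5, 10, 25 and 30. They reproduce exactly under P(Bin(n, 0.20) ≤ x−1) > 0.80, which corresponds to a Beta(0,1) prior, and also under a Beta(1,4) prior. Both use one outcome per patient.

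**Step 2: each patient counted once.** Cumulative probability of suspension by 20 patients, by exact recursion over looks at 5, 10, 15 and 20:

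| true patient rate | printed boundary | boundary from stated prior |
|---|---|---|
| 10% | 0.028 | 0.117 |
| 20% | 0.261 | 0.432 |
| 30% | 0.643 | 0.757 |
| 40% | 0.898 | 0.935 |

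**Step 3: the three-occurrence qualifier.** Simulation with the printed boundary to 20 patients at a true rate of 40%. Assumptions not in the documents: 50% or 75% of affected patients have an organ-type event, spread evenly over the eight systems, and the rest are haematologic.

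| reading | 50% organ-type | 75% organ-type |
|---|---|---|
| no qualifier | 90% | 90% |
| organ events count once 3 have occurred over all organs | 83% | 89% |
| organ events count only in a system that has reached 3 | 32% | 15% |

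**Step 4: repeat events counted separately.** Simulation with 1 + Poisson(m−1) events per affected patient, m assumed, at a true patient rate of 10%. Suspension by 20 patients is 3% at m = 1, 22% at m = 1.5 and 39% at m = 2.

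**Step 5: the backup trigger.** Take the per-system reading in step 3 and add the over-20% single-event trigger. Assume it is checked after every patient from the tenth on, with haematologic events split evenly between neutropenia and thrombocytopenia. If organ toxicity is one category for that trigger, suspension at a 40% rate is about 80% (50% organ-type) and 91% (75%). If that trigger is also split by organ system, it is about 44% and 23%.

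**The case against.** A reader might infer that the plan counts events instead of patients. The text does not establish this. A denominator of treated patients, a toxicity rate that cannot exceed 100%, and a beta posterior all fit one outcome per patient, and nothing says that repeat events in one patient are added up. The step 4 figures show the cost of a reading left open, not of a rule adopted.

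A reader might also infer that the qualifier makes the rule miss an unsafe regimen. That holds only if three occurrences are required in each organ system, which the text does not say. Pooled over organs, the loss is 1 to 7 percentage points. The single-event trigger, the trigger at three treatment-related deaths, and the committee's authority to suspend at any point (Sections 4.7 and 7.4) also stand behind the boundary. The single-event trigger is only a partial backup: it starts at 10 patients, looks at single events and not the composite, and step 5 shows that its value too depends on how organ toxicity is grouped.

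Finally, the 20% phrase might seem to reverse the rule. It is better read as a misplaced ceiling, since the next sentence gives the operative criterion the right way round.

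These points narrow the finding but do not remove it. The qualifier still has no scope and still disagrees with the next trigger.

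**Conclusion.** The concern holds as an inconsistency in a stated safety decision rule. The event, its qualifier and the counting unit are not fixed, and the operating characteristics move widely with the reading: from 90% to between 89% and 15% at a 40% rate under the qualifier, and from 3% to between 22% and 39% at a 10% rate under repeat counting. These ranges rest on the assumed organ-type share, the even spread over systems and the assumed events per patient.

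The two faults push in opposite directions, so the documents support neither a claim that the rule is too lax nor one that it is too strict.

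The mismatch between the printed boundary and the stated prior needs no such assumptions. Counting patients once, it lowers suspension by 20 patients from 43% to 26% at a 20% rate and from 76% to 64% at a 30% rate.

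**What to change.** In Section 11.11:

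1. State that each treated patient counts at most once, and word the boundary as patients with an event out of patients treated.
2. Take the 20% phrase out of the event definition, leaving it in the decision rule, and remove the reference to arms.
3. Reconcile the three-occurrence qualifier with the next trigger. If it stays, state its unit and which categories it covers. Which toxicities qualify is the sponsor's clinical decision.
4. Make the boundary agree with the stated uniform prior and 80% cutoff (2/5, 3/10, 5/15, 6/20, 7/25, 8/30), or state the prior actually used. Report the suspension probabilities for the version adopted.

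The cost is an amendment to one section and a short calculation. No new data are needed.

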3.0 Patient Eligibility

The target population for this phase II study is patients with histologically confirmed (previously untreated) peripheral T-cell lymphoma (PTCL). Northwestern University will serve as the lead site and coordinating center for this study. Participating sites will include Weill Cornell Medical College, and City of Hope.

A total of 20 evaluable subjects will be needed for this trial; up to 35 may be accrued to obtain 20 who are evaluable. Approximately 3 potentially eligible patients are seen per month, and it is anticipated that at least 1 per month will be accrued (once all sites are up and running). Potential patients may be referred to the Principal Investigator (PI) at Northwestern University, , or to the local PI at each participating site.

Eligibility will be evaluated by the study team according to the following criteria. Eligibility waivers are not permitted. Subjects must meet all of the inclusion and exclusion criteria to be registered to the study. Study treatment may not begin until a subject is registered. After registration, treatment should begin with 14 days. Please refer to Section 11.4 for complete instructions regarding registration procedures.

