4.7 Suspension of Accrual

This study will be monitored in accordance with the Data Safety Monitoring Plan (DSMP) of the Robert H. Lurie Comprehensive Cancer Center of Northwestern University. The DSMC will review all toxicity data, and in the event of an excessive toxicity, the DSMC may require suspension of accrual.

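### Section 11.11 contradicts itself: four of the six listed toxicity counts are one event higher than its uniform-prior, 80% posterior rule gives

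*Combined protocol and SAP*

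**What the plan says.** Section 11.11 (Criteria for Suspension in Accrual) schedules a toxicity analysis after every 5 patients. The rule is complete. The section names its method, "Using a Bayesian approach with a non-informative (uniform) prior", and sets the point at which toxicity counts as excessive, namely a "posterior probability of the toxicity rate being greater than 20% exceeds 80" per cent. The next sentence turns this into counts and presents them as the points at which the rule is met: "3 or more excessive toxicity events (as described above) out of 5 treated patients, 4 or more out of 10", then 5 of 15 and 6 of 20, and for the last two looks "8 or more out of 25, or 9 or more out of 30".

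The same section has a second trigger, "Incidence of >20% of any single excessive toxicity event", which needs at least 10 treated patients, and a third for three or more treatment-related deaths. Section 4.7 adds that "in the event of an excessive toxicity, the DSMC may require suspension of accrual", and Section 7.4 gives the DSMC similar discretion. Section 3.0 sets the accrual: "up to 35 may be accrued to obtain 20 who are evaluable".

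**The concern.** A uniform prior, a 20% limit and an 80% posterior cut-off fix the counts completely, so the list can be checked without any outside figure. Three events in five patients is a 60% observed rate, which looks late for a rule that asks only for 80% certainty that the rate is above 20%.

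Section 11.11 lists criteria that trigger suspension of accrual, and this is its only probability-based toxicity rule. Appendix E (Amendment 3) records that the 20% limit and the 80% posterior probability were adopted to meet an FDA requirement during review of a clinical hold. If the counts do not carry out that criterion, a DSMC working from the list would let accrual continue at points where the stated criterion suspends it.

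**Working it through.** **Inputs, all from Section 11.11.** Prior Beta(1,1); limit 0.20; cut-off 0.80; looks at n = 5, 10, 15, 20, 25, 30; listed counts 3, 4, 5, 6, 8, 9.

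**Formula.** With x events in n patients the posterior is Beta(1+x, 1+n−x). For whole numbers, P(rate > 0.20) = P(Y ≤ x), where Y is Binomial(n+1, 0.20). The boundary is the smallest x for which this exceeds 0.80.

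**One case by hand.** n = 5, x = 2: P(Y ≤ 2) for Binomial(6, 0.20) = 0.2621 + 0.3932 + 0.2458 = 0.9011. This is above 0.80, so 2/5 already meets the stated rule.

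**All six looks.**

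| n | Listed count | Posterior two below | Posterior one below | Posterior at listed count | Count from stated rule |
|---|---|---|---|---|---|
| 5 | 3 | 0.6554 | 0.9011 | 0.9830 | 2 |
| 10 | 4 | 0.6174 | 0.8389 | 0.9496 | 3 |
| 15 | 5 | 0.5981 | 0.7982 | 0.9183 | 5 |
| 20 | 6 | 0.5860 | 0.7693 | 0.8915 | 6 |
| 25 | 8 | 0.7474 | 0.8687 | 0.9408 | 7 |
| 30 | 9 | 0.7300 | 0.8492 | 0.9254 | 8 |

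The listed counts at 15 and 20 are reproduced. Those at 5, 10, 25 and 30 are each exactly one event too high.

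**Could another cut-off explain the list?** Not with a uniform prior. Leaving out 2/5 needs a cut-off of at least 0.9011; including 6/20 needs one below 0.8915.

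**Could another method?** Yes, several. Beta(1,4), Beta(0.6,2.4) and Beta(0.8,3.2) priors with the 80% cut-off each return 3, 4, 5, 6, 8, 9. So does the smallest x with P(X ≥ x | n, 0.20) < 0.20. The documents do not say which was used, so none can be assumed.

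**Effect on suspension.** Exact binomial recursion with a look every 5 patients, independent patients and at most one counted event per patient. In the last two columns the parallel trigger is read as applying to all event types together, so that it fires when x/n > 0.20 from n = 10 (3/10, 4/15, 5/20, 6/25, 7/30).

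| True rate | By patient | Listed | Stated rule | Listed + parallel | Stated rule + parallel |
|---|---|---|---|---|---|
| 30% | 5 | 16% | 47% | 16% | 47% |
| 30% | 10 | 37% | 67% | 62% | 67% |
| 30% | 20 | 64% | 76% | 82% | 84% |
| 40% | 5 | 32% | 66% | 32% | 66% |
| 40% | 10 | 64% | 86% | 83% | 86% |
| 40% | 20 | 90% | 94% | 96% | 97% |
| 20% | 20 | 26% | 43% | 48% | 52% |
| 15% | 20 | 11% | 26% | 27% | 32% |
| 10% | 20 | 3% | 12% | 10% | 14% |

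**The case against.** The best defence is that other provisions close the gap.

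- **Parallel trigger.** Read as applying to all event types together, the trigger for incidence above 20% covers every mismatch from patient 10 on, and the remaining difference is 5 points or less at true rates of 30% and 40%. That stands on this reading. Its wording also allows counting each event type separately, and then a mixture of types is not covered. On either reading it is silent at 2/5.
- **Floor of three.** The event definition contains an unclear phrase requiring at least three occurrences. If it sets a minimum of three events, the listed 3/5 is right. This could excuse the first look only; at 10, 25 and 30 the stated rule already needs 3, 7 and 8 events. The text also derives all six counts from the posterior rule, not from a floor.
- **Sufficient, not minimal.** Read literally, the counts might merely be enough to meet the rule. But 5/15 and 6/20 are exact minima, so the list is evidently meant as the boundary.
- **DSMC oversight.** The committee reviews toxicity every two weeks and may suspend accrual when it sees fit, and a suspension can be lifted. This softens the consequence but does not settle which sentence governs.
- **Reach.** With a goal of 20 evaluable patients, the looks at 25 and 30 may not occur. They can, since up to 35 may be accrued. The looks at 5 and 10 come well within the goal.
- **Event counting.** If one patient can contribute several events, the suspension percentages do not apply. The mismatch in the counts remains for a per-patient rate.

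**Conclusion.** The rule and the counts in Section 11.11 cannot both be right. Four of the six counts are one event above what the stated prior and cut-off give, and no other cut-off with that prior rescues the list. The arithmetic rests only on figures in the section.

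The practical effect is largest at the first look: 16% versus 47% chance of suspension at a true rate of 30%, and 32% versus 66% at 40%. No other event-rate trigger operates there, unless the three-occurrence phrase is taken as a floor. From patient 10 the size depends on the parallel trigger: 30 points (37% versus 67%) at a true rate of 30% if it is ignored, 5 points (62% versus 67%) if it applies to all event types together. The separate-type reading was not quantified. This is an error in a safety threshold as written and should be corrected. The documents do not show whether the rule or the list was intended.

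**What to change.** Make the rule and the counts in Section 11.11 agree, in one of two ways:

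1. Keep the uniform prior and the 80% cut-off, and list 2/5, 3/10, 5/15, 6/20, 7/25, 8/30.
2. Keep the listed counts, and have the study statistician state the prior or tail rule that produced them.

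In either case, say whether the trigger for incidence above 20% is counted per event type or over all types, clarify the three-occurrence phrase, and notify the DSMC. A short table of suspension probabilities for the combined rules would help the committee but is not needed to remove the contradiction.

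The edit is one or two sentences and a notice. The first option brings more suspensions by patient 20 when the true rate is at or below the limit: 17 points more at a true 20% (43% versus 26%) without the parallel trigger, or 4 points more (52% versus 48%) with it applied to all types. Under the second, the plan can no longer describe the counts as coming from a non-informative prior with an 80% posterior rule.

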Objectives	 Primary Evaluate the efficacy of romidepsin plus lenalidomide in patients with PTCL; this will be done by evaluating the objective response rate by Cheson criteria. Secondary objectives: Evaluate safety (as defined by frequency and severity of toxicity events). Further evaluate efficacy as measured by PFS and OS measured at 1 and 3 years after beginning treatment. Further evaluate efficacy as measured by duration of response and time to first cytotoxic chemotherapy. Exploratory objectives: Further evaluate the use of NM PET/CT vs CT imaging in PTCL. Validate a new prognostic model for newly diagnosed PTCL. 		
	3. Investigate the tumor immunohistochemical profile to identify potential biomarkers associated with prognosis and treatment response		
Study Population	Up to 35 adult patients with previously untreated PTCL (see specific histologic subtypes in Schema and Section 3.0) may be enrolled to obtain 20 evaluable patients.		
Treatment Plan	 Patients will receive treatment in cycles defined as 28 days each: Romidepsin 10 mg/m² IV on days 1, 8, and 15 of each cycle (dose escalated to 14 mg/m² if tolerated first 6 doses) Lenalidomide 25 mg PO daily days 1- 21 of each cycle Patients may receive treatment for up to 1 year (unless discontinued prior to that for progression of disease, intolerable toxicity, or withdrawal of consent) 		
Statistical Methodology	The study will analyze n=20 evaluable patients. This will allow us to estimate the underlying true response rate with a half width of an approximate 95% confidence interval equal to 1.96x0.5/sqrt(20) = 1.96x0.11 = 0.22.		

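### The composite toxicity rule in Section 11.11 ends at 30 treated patients with an instruction to continue, although up to 35 may be accrued

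*Combined protocol and SAP*

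**What the plan says.** Section 11.11 defines a composite excessive-toxicity event: grade 4 or worse neutropenia or thrombocytopenia, or grade 3 or worse organ toxicity, at least possibly related to the regimen. On timing it says: "After every 5 patients an interim analysis will be performed to determine whether there is excessive toxicity". The method is given as "Using a Bayesian approach with a non-informative (uniform) prior", and the study is judged to show "excessive toxicity if the posterior probability of the toxicity rate being greater than 20% exceeds 80" percent. The printed counts are 3 or more "out of 5 treated patients, 4 or more out of 10, 5 or more out of 15, 6 or more out of 20", followed by 8 of 25 and 9 of 30. The paragraph closes: "If, by 30 patients treated, the study has not been terminated for toxicity, it will continue to the goal accrual".

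On size, Section 3.0 states: "A total of 20 evaluable subjects will be needed for this trial; up to 35 may be accrued to obtain 20 who are evaluable". The Study Summary gives the same ceiling ("Up to 35 adult patients with previously untreated PTCL"), and Section 1.4 repeats it for patients treated.

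The same list in 11.11 has two other numeric triggers for suspending accrual, neither with an upper limit on the number treated. One is an incidence above 20% of a single excessive toxicity event, from 10 treated onwards. The other is three treatment-related deaths. The Data and Safety Monitoring Committee (DSMC) analyses toxicity every two weeks (11.11), and Sections 4.7 and 7.4 let it suspend accrual.

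**The concern.** The ceiling is five patients beyond the last printed count, and the text does not merely fall silent there. It directs the study to carry on. Read literally, a composite toxicity rate that would have suspended accrual at 30 has no such consequence at 31 to 34.

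The same applies to events that arise after the look at 30 in patients already counted. Treatment can last a year, and Section 4.1.1 permits a higher romidepsin dose after six doses, so later events are to be expected. At stake is whether the one rule that pools the toxicity types keeps running for as long as new patients can be exposed.

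**Working it through.** **Inputs.** From 11.11: uniform prior, toxicity threshold 0.20, posterior cut-off 0.80, looks every 5 patients, printed counts 3, 4, 5, 6, 8, 9. From 3.0: 20 evaluable, cap 35. The documents give no evaluability rate, so a range is assumed.

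**Step 1: the plan's own counts.** With x events in n patients, P(rate > 0.20) = 1 − F(0.20; 1 + x, 1 + n − x), where F is the Beta distribution function. The rule needs the smallest x for which this exceeds 0.80.

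| n | printed | by the stated rule | posterior there | posterior one event lower |
|---|---|---|---|---|
| 5 | 3 | 2 | 0.901 | 0.655 |
| 10 | 4 | 3 | 0.839 | 0.617 |
| 15 | 5 | 5 | 0.918 | 0.798 |
| 20 | 6 | 6 | 0.891 | 0.769 |
| 25 | 8 | 7 | 0.869 | 0.747 |
| 30 | 9 | 8 | 0.849 | 0.730 |
| 35 | none | 9 | 0.832 | 0.716 |

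The printed list is not reproduced at 5, 10, 25 and 30, where it is one event higher than the wording implies. A Beta(1,4) prior with the 0.80 cut-off does reproduce it, as does an exact binomial tail of at most 0.20. Both give 10, not 9, at 35.

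**Step 2: the window from 31 to 34.** Nine events, the last printed count, give posteriors of 0.910, 0.893, 0.875 and 0.854 at n = 31, 32, 33 and 34. All exceed 0.80, so each meets the stated definition of excessive toxicity while the text says to continue.

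**Step 3: what the remaining triggers catch.** More than 20% means 7 or more events at 31 to 34 treated (0.20 × 31 = 6.2; 0.20 × 34 = 6.8) and 8 or more at 35 (0.20 × 35 = 7). Read per toxicity type, this can miss a spread. Suppose 4 neutropenia, 3 thrombocytopenia and 3 hepatic events in ten different patients among 34, with 8 of the ten by the look at 30. The largest single type is 4/34 = 12%, the composite is 10/34 = 29%, and the posterior is 0.925. No numeric trigger fires.

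**Step 4: how often 30 is exceeded.** Fewer than 20 evaluable among 30 treated means at most 19, so at least 11 non-evaluable. With q the assumed evaluable rate among treated patients, the probability is P(Bin(30, q) ≤ 19):

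- q = 0.90: 0.0001
- q = 0.85: 0.003
- q = 0.80: 0.026
- q = 0.75: 0.106
- q = 0.70: 0.270
- q = 0.65: 0.492

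**Step 5: what carrying the count forward would do.** This is an exact binomial recursion over the printed looks, with one yes/no outcome per patient known at each look. It conditions on the trial passing the look at 30 and going on to 34 treated.

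| true rate | passes all looks to 30 | passes and reaches 9 by patient 34 | ratio |
|---|---|---|---|
| 20% | 0.713 | 0.050 | 0.07 |
| 30% | 0.286 | 0.082 | 0.29 |
| 40% | 0.054 | 0.029 | 0.55 |

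**The case against.** The strongest reply is that patients 31 to 35 are not left unwatched. The single-event and three-death triggers have no upper limit, the DSMC analyses toxicity every two weeks, and it may suspend or close accrual at any point. The closing sentence belongs to the Bayesian paragraph and cancels none of this. If the single-event trigger were read as covering the composite, its 7 events at 31 to 34 would be stricter than 9. All of that stands except the last step: the wording points to one kind of event, and on that reading Step 3 shows what it can miss. Committee discretion is also weaker where the only written guidance on the composite is to continue.

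Second, with looks every five patients, the look at 30 is the last that can affect accrual, because the next falls at the cap. This stands, and it defeats any call for a look at 35 as a suspension rule. It does not answer the case for carrying the last count through 31 to 34.

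Third, the situation may be remote. Appendix E shows that the cap of 35 was paired with a target of 32 evaluable before Amendment 8, and 32/35 is 91%. At 90% the chance of passing 30 is about 0.0001. Patients registered but never treated also use places under the cap without counting as treated; five of them would hold the treated number to 30. This stands and limits the size of the point.

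A reader might also infer that many non-evaluable patients signal poor tolerability. Section 4.6 does not support that: patients withdrawn early for toxicity or progression remain evaluable, so passing 30 is driven by other dropout.

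**Conclusion.** The point holds in a limited form. The composite rule stops at 30 treated with an instruction to continue, while up to 35 may be accrued, so it covers neither patients 31 to 35 nor late events in the first 30. A reader might infer that these patients have no toxicity boundary at all. The documents do not support that, because two numeric triggers and committee review remain.

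The consequence is small overall: about 0.0001 to 0.27 probability of entering the window for evaluable rates from 90% down to 70%, all assumed. Within the window it is not negligible. For trials that pass the look at 30 and reach 34 treated, a carried-forward count of nine would flag 29% at a true rate of 30% and 55% at 40%. Those figures assume one binary outcome per patient, known at each look, and ignore late events. The mismatch between the printed counts and the stated prior and cut-off is a separate and larger fault in the same paragraph. It bears here because it leaves the count beyond 30 undetermined (9 or 10 at 35).

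**What to change.** Delete the closing sentence of the Bayesian paragraph in 11.11. Replace it with a statement that the composite posterior criterion, with the last count, stays in force while accrual is open, alongside the other 11.11 triggers.

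Do not add a look at 35 as a suspension rule. Do not print any count beyond 30 until the existing counts are reconciled with the uniform prior and 80% cut-off. If the accrual cap is lowered, end the list at the new cap.

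The cost is one changed sentence, slightly more DSMC work, and a slightly higher chance of a false suspension. At a true rate of exactly 20%, about 7% of trials that pass the look at 30 and go on to 34 treated would be flagged (0.050/0.713).
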